Student Research Project Proposal

Title:

Carbon Dioxide (CO₂) Clearance from various face masks in Normal Volunteers at various level of Expiratory Positive Airway Pressure (EPAP) when Using a Non-Invasive Positive Pressure Ventilation (NIPPV)

Investigators:

Mentor:

[name], MHS, RRT, FAARC, FCCP

Graduate Student:

[name], Respiratory Care Department, Rush University.

Study aim:

Determine the EPAP (baseline pressure) required to effectively wash out CO₂ for current available masks, and assess perceived level of comfort with each mask with using noninvasive ventilator.

1- Abstract:

Background: Noninvasive positive pressure ventilation (NIPPV) can be delivered via single limb circuit or double limb circuit ventilators. There are many advantages to NPPV. However, a reasonable number of questions remain unanswered, such as mask impact on carbon dioxide (CO₂) clearance based on EPAP level.

Objective: Determine the EPAP (baseline pressure) required to effectively wash out CO₂ for each mask, and assess perceived level of comfort with each mask with ICU ventilator.

Method: This study will be a randomized crossover trial that will be conducted at Rush University. The study will be conducted with 20 healthy volunteers who will be placed on ICU ventilator operating in the NIPPV mode. All subjects will perform 15 minutes of breathing on NIPPV on each mask of the 4 different masks (2 oronasal and 2 full face masks) that are randomly selected. Breathing through each mask will be followed by a 5-minute wash out period between masks. End tidal Carbon Dioxide (EtCO₂) will be sampled nasal/oral. Different levels of EPAP will be set and CO₂ clearance will be monitored. Additionally, subjective mask comfort will be assessed via visual analog scale (VAS) with 1 referring to least comfortable and 5 being the most comfortable.

2- Introduction

Noninvasive positive pressure ventilation (NIPPV) is a form of ventilatory support for spontaneously breathing patients without the need of an artificial airway.¹ NIPPV is recommended for patients with chronic obstructive pulmonary disease (COPD) exacerbation as well as cardiogenic pulmonary edema.² The use of NIPPV has reduced the need for intubation and improved mortality.² Some studies have demonstrated a decrease in mortality rate in individuals with acute hypoxic respiratory failure and immunosuppression with the use of NIPPV.² Issues that exist with NIPPV is patient compliance or tolerance.³ NIPPV failure rates can exceed 40%. Mask intolerance remains a major hindrance to NIPPV success.^{3,4}

NIPPV uses external interfaces such as nasal mask, facial mask, mouthpiece, or helmet.¹ Noninvasive ventilation (NIPPV) can be delivered by a dedicated NIPPV ventilator which utilizes a single limb circuit requiring an expiratory port to allow for carbon dioxide clearance. This NIPPV ventilator has the ability to adjust for leak and continue to function properly without the mask fitting tightly to the face.^{3,4} NIPPV can also be delivered by ICU ventilators which utilize a dual limb circuit and these circuits usually have no leak to properly function. NIPPV interface fitting is another key factor, however, to minimize leak the interface may be over tighten and cause patients discomfort. Patients may complain of NIPPV due to multiple factors, it can be facial discomfort, massive air leak or pressure sores.⁵ It has reported that oronasal mask to perform worse with pain at nose bridge in comparison to total face mask.⁶ While cheeks' pain was more prevalent in the oronasal mask in comparison to total face mask⁷, oronasal dryness and claustrophobic were reported higher with total face mask.⁶ It is fair to state that success of NIPPV is dependent on many factors, one of them is mask characteristics.⁸ These issues may

decrease patient tolerance of NIPPV.⁵ A properly fit mask may increase patient compliance. Moreover, health care providers (HCPs) must have an excellent understanding of NIPPV and the skills to execute the task successfully.⁵ However, a concern remains that a single limb circuit with NIPPV ventilators may cause carbon dioxide (CO₂) rebreathing.⁹ This CO₂ rebreathing can lead to NIPPV failure.

Samolski et al, studied the CO₂ rebreathing while using a portable ventilator which uses a single limb circuit. They studied the effect of expiratory port location, different sites of the port (i.e. in the mask, before the mask), and the addition of dead space between the circuit and mask on CO₂ rebreathing. They found no CO₂ rebreathing, and baseline pressure as low as 4 cm H₂O was effective in preventing CO₂ rebreathing.⁹ However, this study has limitations. First, they used three different nasal masks and 2 different facial masks. Currently there are newer masks available that need testing. Last, they measured fraction of inspired CO₂ (FiCO₂) via a sampling line located in the mask.⁹ The site of sampling can significantly affect the accuracy of end tidal CO₂ (EtCO₂) measurement. Sampling line at the oral/nasal site may be the most reliable sampling site for EtCO₂ and determining rebreathing of exhaled gas.

NIPPV interface choice is crucial to achieve a good clinical outcome with the use of NIPPV. Common interfaces are nasal mask which covers the nose only, facial mask known as oronasal mask which covers the nose and mouth. Total face mask and helmet are gaining popularity. Generally, nasal mask is better tolerated, while oronasal mask is more effective for improving gas exchange. The perfect mask should be lightweight, comfortable, easy to apply, transparent in color, latex-free, have small internal volume and low airflow resistance.¹

The total face mask which covers the entire face was designed with the aim of enhancing patient tolerance. Newer generation of NIPPV full face masks are available on the market (e.g. PerforMax) which also covers the eyes, nose, and mouth. The mask also, has advantages by minimizing gas leakage. Furthermore, due to its shape, it helps to minimize pressure sores on the face as there is no contact with the nose bridge. On the other hand, the mask has disadvantages such as adding a large dead space, which varies from mask to mask based on different manufacturers. Unlike the larger older generation, this mask comes without the two orifices for CO₂ washout.^{3,6} To accommodate both types of ventilators (NIPPV and ICU ventilators) this mask comes with two options of an elbow, a standard elbow for use with double circuit ICU ventilators or an entrainment elbow for NIPPV ventilators.³ It is worth mentioning that the total face mask costs more than the nasal mask or oronasal mask.¹⁰ Despite total face mask's large internal volume, the mask doesn't affect patients' gas exchange during short term of NIPPV using ICU ventilator.¹⁰

NIPPV masks were developed with an intentional leak to remove CO₂ from the interface.⁸ A comparison of three different masks (mask A, mask B, mask C) on healthy volunteers to investigate CO₂ wash out hypothesized that in NIPPV masks with lower rates of intentional leaks, CO₂ rebreathing might occur.⁸ Transcutaneous capnography (PtcCO₂) was measured. IPAP level of 14 cm H₂O, EPAP of 4 cm H₂O was applied to all masks. Each subject was placed on NIPPV, and tried all three masks consecutively. Each mask was tested for 10 minutes followed by 5 minutes break in between masks. They found no differences in PtcCO₂ between masks.⁸ Despite accuracy of PtcCO₂ measurement, this study has some limitations. It did not assess CO₂ clearance at the mask

via EtCO₂. Masks B & C both had higher rate of total leaks due to higher rate of unintentional leaks which may improved CO₂ wash out, hence, led to no differences in PtcCO₂.⁸ Another study compared total face mask against oronasal mask impact on gas exchange (PvCO₂) favors total face mask in the first 6 hours and during the acute phase of respiratory failure using NIPPV.⁷ Both Medrinal and Sadeghi assessed gas exchange not masks' CO₂ clearance. Since the intentional leak impacts CO₂ clearance, and the intentional leak level depends on the level of pressure.⁸ The previous studies didn't study different level of EPAP (baseline pressure). One level of EPAP pressure of 4 cm H₂O was used in Medrinal study based on Samolski's finding.⁸ While in Sadeghi's study, IPAP started at 10 cm H₂O and EPAP started at 4 cm H₂O. IPAP and EPAP were increased gradually based on subjects' need, therefore it lacked consistency in EPAP level.⁹

ICU ventilators using double limb circuit is an alternative to deliver NIPPV, however, researches on minimum baseline pressure required to prevent CO₂ rebreathing is not clear as well. In a study that compared 3 types of masks (2 ONM and 1 FFM) to helmet in acute hypercapnia respiratory failure. NIPPV in both group improved arterial blood gases. ICU ventilators settings in masks group used positive end expiratory pressure (PEEP) referring to baseline pressure that ranged from 3 – 5 cm H₂O (mean 4.26 ± 1.92); and inspiratory pressure adjusted to achieve tidal volume of 6-8 ml/kg (16.37 ± 4.19). On the other hand, settings for helmet groups were ~ 30%.¹¹

The answer regarding effective EPAP level to wash out CO₂ remains uncertain. The purpose of this study is to compare the efficacy of CO₂ clearance between different NIPPV interfaces (oronasal and full face masks) when using double limb circuit ICU

ventilator at lower levels of EPAP. The aim of this study is to determine the EPAP (baseline pressure) required to effectively wash out CO₂ for each mask and assess perceived level of comfort with each mask.

3- Methods:

This study will be a randomized crossover trial that will be conducted at Rush University.

Normal volunteers will be recruited from Rush University Medical Centers. Volunteers will be screened with inclusion and exclusion criteria and an informed consent is required in order for them to participate. Demographic (age, gender, ethnicity) will be obtained.

Also, initial baseline vital signs (heart rate, blood pressure, respiratory rate, and oxygen saturation) will be obtained. EtCO₂ will be obtained at baseline and periodically using an oral/nasal sample line with the CapnostreamTM 20p monitor (Medtronic, Minneapolis, MN). The study will use a double limb circuit ICU ventilator Puritan BennettTM (Medtronic, Dublin, Ireland).

We will evaluate 4 NIPPV masks (2 oronasal masks and 2 full face masks).

[figure not shown]
Oronasal masks will be labeled as group A and numbered as A1 and A2; while full face masks will be labeled group B and numbered as B1 and B2. Order of the masks will be randomly chosen in two steps. First steps will be choosing A or B then randomly assign mask in each of these groups. We will randomly assign mask in group A or B by drawing an initial mask from the group and then continue the sequence of masks from that point.

For example, we randomly chose group A, then randomly chose A2, the sequence will be A2, A1. Then we would randomly choose B2, then the sequence would be B2, B1.

All subjects will perform 15 minutes on each mask followed by 5 minutes wash out interval between masks. EPAP levels will be 0, 2, 4, & 5 while IPAP remains at 5 higher than EPAP. EtCO₂ will be collected at 4:00, 4:30 and 5:00 minute mark. These three measures should differ by less than 20% of their average. Also, subjective mask

comfort will be assessed via visual analog scale (VAS) with 1 referring to least comfortable and 5 being the most comfortable after 5 each EPAP setting.

Procedure figure:

4- Subject Population:

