4.4.2. Facial surgery or deformity

4.4.3. Ear infection

4.4.4. History of pulmonary or cardiac disease

5- Research recruitment and Consent Procedures:

5.1. Subjects will be recruited from students enrolled, faculty, and staff at Rush University.

5.2. An informed consent will be obtained by the investigators for all eligible candidate that meet the criteria.

6- Compensation:

Volunteers will be compensated with \$ 25 Visa gift card

7- Special precautions:

- 7.1. Subjects refrain from eating at least 60 min before the study
- 7.2. Study will be stopped if HR change by 20% from baseline for more than 1 min.
- 7.3. Study will be stopped if subjects complain of shortness of breath

8- Confidentiality:

Subject names, date of birth, and contact information (email) will be stored in REDCap. However, only de-identified data will be used for analysis.

9- Data Collection Instruments/ Data Collection Procedures/Data Analysis Plan:

Data for each subject will be recorded in REDCap

10- Variables:

Dependent: CO₂ clearance, level of comfort-

Independent: NIPPV interface, level of EPAP

11- Limitation:

It is performed on healthy subjects.

12- Analysis:

Data will be recorded in REDCap. Demographics data age (interval), gender (nominal),

ethnicity (nominal) will be collected. HR (continuous), RR (continuous), SpO2

(continuous), ETCO₂ (continuous), EPAP (ordinal), IPAP (ordinal) will be collected.

Means and Standard deviations will be calculated for aforementioned data. NIPPV interfaces number, sizes will be collected. Level of comfort will be collected; median and interquartile ranges will be calculated. Relationship between dependent variable ETCO₂ and independent variable EPAP level will be analyzed by a Kruskal-Wallis test to determine if a significant difference exists. If a significant difference is found a Mann-Whitney U Test will be used to determine which EPAP levels significantly differ. Relationship between dependent variable comfort level and independent variable NIPPV interfaces will be analyzed a Kruskal-Wallis test to determine if a significant difference exists. If a significant difference is found a Mann-Whitney U Test will be used to determine which masks were significantly more comfortable.

Literature cited:

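### No stated analysis compares EtCO₂ between masks or tests mask-by-EPAP, although comparing masks on CO₂ clearance is the study's stated purpose

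*Combined protocol and SAP*

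**What the plan says.** - **Purpose and aim (section 2, Introduction).** The purpose is comparative: "The purpose of this study is to compare the efficacy of CO₂ clearance between different NIPPV interfaces". The aim follows directly: "determine the EPAP (baseline pressure) required to effectively wash out CO₂ for each mask".
- **Open question (section 1, Abstract).** The background names as unanswered "mask impact on carbon dioxide (CO₂) clearance based on EPAP level".
- **Rationale (section 2).** One earlier comparison of three masks is criticised: "It did not assess CO₂ clearance at the mask". Full face masks are said to have the drawback of "adding a large dead space, which varies from mask to mask based on different manufacturers".
- **Variables (section 10).** CO₂ clearance and comfort are the dependent variables. The others are given as "Independent: NIPPV interface, level of EPAP".
- **Analysis (section 12).** For EtCO₂: "Relationship between dependent variable ETCO₂ and independent variable EPAP level will be analyzed by a Kruskal-Wallis test", with Mann-Whitney follow-up between EPAP levels. Mask appears as a factor only for comfort, also by Kruskal-Wallis with Mann-Whitney follow-up. EtCO₂ is otherwise summarised by mean and SD, with no statement that this is done by mask.

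**The concern.** Two dependent and two independent variables give four possible pairings. Section 12 covers EtCO₂ by EPAP and comfort by mask. The pairing that carries the purpose, EtCO₂ by mask, is missing, and so is any analysis of whether the EPAP effect differs between masks.

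EtCO₂ will be measured on all four masks in all 20 subjects. Any statement about which mask clears CO₂ better would nevertheless be unplanned, with the model, the contrasts and the multiplicity rule chosen after the data are seen. The choice is wide: 6 mask pairs × 4 EPAP levels = 24 between-mask contrasts. A non-significant EPAP test could also be misread as showing that the masks perform alike.

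**Working it through.** **1. Plan's own figure.** The only design figure is 20 subjects (section 4.2). No alpha, power, effect size or SD is given, so it cannot be reproduced. The main check is a reading of section 12 against sections 1, 2 and 10.

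**2. Purpose and aim against the tests**

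| Question | Stated test in section 12 |
|---|---|
| EtCO₂ between masks (purpose) | None |
| EPAP effect on EtCO₂ for each mask (aim) | EPAP test, if run per mask; not stated |
| Whether the EPAP effect differs by mask | None |
| Comfort between masks | Kruskal-Wallis by mask |

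**3. Why the EPAP test cannot stand in for a mask test.** Suppose one mask raises EtCO₂ by a constant c at every EPAP level.
- *Per mask:* adding c to all of a mask's values leaves every rank unchanged, so the Kruskal-Wallis H is unchanged. On one simulated mask, H = 0.1754 with 0, 1.5, 3 or 100 mmHg added.
- *Pooled:* each EPAP group holds 20 × 4 = 80 values, 20 from each mask, so all four groups shift alike. With no EPAP effect their distributions stay equal, and the test rejects no more often than by chance.

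Neither argument depends on sample size or SD.

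**4. Illustration (assumed SDs; the documents give none).** EtCO₂ = 38 + subject (SD 4) + subject-by-mask (SD τ) + residual (SD = SDdiff/√2) + mask effect, in mmHg. SDdiff, the within-subject difference SD, is 2 or 3, and τ is 0 to 1.5. There are 20 subjects × 4 masks × 4 EPAP levels. Mask order follows the two-step draw in section 3 (2 × 2 × 2 = 8 sequences). The mask test uses subject-by-mask error and adjusts for period.

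| Constant full-face excess of 1.5 mmHg | Detected |
|---|---|
| Planned EPAP test | about 0% |
| Within-subject mask test | about 83–100% |
| Friedman by mask at one EPAP, alpha 0.0125 | 22–81% |

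The planned test falls below a nominal 5% because Kruskal-Wallis ignores the pairing within subjects. A well-calibrated EPAP test would give about 5%, which is still only chance.

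**5. Which random effects are needed**
- Subject only: 10–45% false positives for mask at τ = 0.5–1.5. With subject-by-mask added: 4–6%.
- Subject and subject-by-mask, but no subject-by-EPAP: if subjects also differ in EPAP response (SD 0.5–1.5, assumed), the EPAP test has 8–40% false positives and the mask-by-EPAP test only 0–4%. Both interaction terms with subject are therefore needed.

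**6. Precision and the price of multiplicity.** Half-width = t × SD/√20 on 19 df, with Bonferroni as an approximation.
- Between-mask contrast at one EPAP: SD = √(SDdiff² + 2τ²), from √4 = 2.00 to √(9 + 4.5) = 3.67. Unadjusted (t = 2.093): 0.94–1.72 mmHg. For 24 contrasts (t = 3.561): 1.59–2.93. For 48 (t = 3.866): 1.73–3.18.
- Averaged over EPAP: SD = √(2(τ² + SDdiff²/8)), from 1.00 to 2.60. Unadjusted: 0.47–1.22. For 6 contrasts (t = 2.944): 0.66–1.71.
- Width ratios: 2.944/2.093 = 1.41; 3.561/2.093 = 1.70; 3.866/2.093 = 1.85.

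Subject-by-EPAP variation cancels from a between-mask contrast at the same EPAP, so these widths hold with that term present.

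**The case against.** The strongest reply is that the study is mainly about EPAP. The study aim, the Abstract's objective and the Introduction's aim all ask what EPAP each mask needs, and comparing masks is called the purpose only once. The Introduction also faults earlier work for not varying EPAP. On that view the EPAP test, run per mask, is the right main analysis. This stands in part: a per-mask run would serve the aim, and the aim should not rank below the purpose. It does not supply the comparison, because four separate per-mask results do not compare masks.

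A second reply is that a mask difference may be small. The Introduction reports no short-term effect of the total face mask on gas exchange with an ICU ventilator, and says dual-limb circuits usually run without leak. That bears on the likely result, not on whether the stated purpose has a test.

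Two stronger readings are tempting, and neither is supported.
- *That the plan has no EPAP analysis for each mask.* Section 12 is silent on pooling, so a per-mask run remains open.
- *That the missing mask term makes the EPAP test weak when a mask difference varies with EPAP.* The Introduction makes such variation plausible: "Since the intentional leak impacts CO₂ clearance, and the intentional leak level depends on the level of pressure". In that case, however, the EPAP test can react. In simulations with a 3 mmHg full-face excess at the lowest EPAP only, a Friedman test by EPAP with no mask factor rejected in 98–100%. The low rejection by Kruskal-Wallis there comes mainly from ignoring pairing, which is a separate defect. The limit that remains is one of interpretation: a pooled rejection does not say which mask is responsible.

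Finally, this is a student project in healthy volunteers and the cure is a change of wording. That limits the cost of the fix but leaves the gap as it is.

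**Conclusion.** The concern holds. Section 12 contains no comparison of EtCO₂ between masks and no mask-by-EPAP test, so the stated purpose has no planned analysis. The aim is served in part, and only if the EPAP test is run per mask. That a constant mask difference cannot show in the EPAP test follows from the design and needs no assumed figure. The contrast of about 0% with about 83–100% for a 1.5 mmHg excess rests on the assumed SDs and on complete data at all four EPAP levels on all four masks. It shows that 20 subjects could support a useful mask comparison under those assumptions, not that masks differ. Section 12 should be corrected before the data are analysed.

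**What to change.** Amend section 12 as follows.

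1. **Model.** Analyse EtCO₂ within subject, with fixed effects for mask, EPAP, mask-by-EPAP and mask period, and random effects for subject, subject-by-mask and subject-by-EPAP. Equivalently, test mask against subject-by-mask and EPAP against subject-by-EPAP.
2. **Simpler alternative.** Use Friedman tests by mask at each EPAP and by EPAP within each mask. These do not adjust for period and have less power for a constant mask difference.
3. **Reporting.** Give the 16 mask-by-EPAP means with confidence intervals.
4. **Multiplicity.** Prespecify two families with Holm control: EPAP contrasts within each mask (the aim; 6 × 4 = 24) and between-mask contrasts (the purpose; 24 by EPAP level, or 6 if averaged over EPAP). Do not rank the aim below the purpose.

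**Cost.** No extra subjects or measurements are needed, only new wording and modest extra analysis. By the Bonferroni approximation, adjusted intervals are about 1.4 times (6 contrasts), 1.7 times (24) or 1.85 times (48) the unadjusted width. The subject-by-mask term also costs power. In the least favourable simulated case (SDdiff 3, τ 1.5) detection of 1.5 mmHg falls from 98% to 83%, but the subject-only model there has 30% false positives.

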4.2. Sample Size

20 healthy subjects.

4.3. Inclusion criteria:

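### The two-step mask draw always runs same-type masks back to back and leaves period balance over 20 volunteers to chance, and the planned tests have no subject or period term to correct for it.

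*Combined protocol and SAP*

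**What the plan says.** Section 3 (Methods) describes the trial as follows: "This study will be a randomized crossover trial that will be conducted at Rush University". There are two oronasal masks (A1, A2) and two full face masks (B1, B2). The order is drawn by type first: "First steps will be choosing A or B then randomly assign mask in each of these groups". Within a type, the order is set by "drawing an initial mask from the group and then continue the sequence of masks from that point". The worked example confirms that partners are adjacent: "the sequence will be A2, A1. Then we would randomly choose B2, then the sequence would be B2, B1". Timing is given as: "All subjects will perform 15 minutes on each mask followed by 5 minutes wash out interval between masks".

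Section 4.2 sets the sample at "20 healthy subjects". No blocking, square or fixed number per sequence is stated, and the text does not say outright that the draw is repeated for each volunteer. The procedure figure is not available in the text reviewed and may hold more detail on order.

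The end of the Introduction gives the purpose as comparing CO₂ clearance between oronasal and full face masks, with comfort assessed for each mask. Section 12 (Analysis) tests comfort by mask, and EtCO₂ by EPAP level, each with Kruskal-Wallis followed by Mann-Whitney. None of these tests has a subject, period, sequence or carry-over term.

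**The concern.** In every order that the draw allows, one mask type fills periods 1 and 2 and the other fills periods 3 and 4. Within a volunteer, any change over the session therefore lines up with mask type. Whether it cancels over the trial depends on how evenly the 20 volunteers split between oronasal first and full face first, and nothing controls that split.

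The documents make such a change plausible. Section 4.4.1 excludes people who have had NIPPV as patients, so volunteers may become used to it as the session goes on. The Introduction also reports discomfort specific to mask type, such as nose-bridge pain with oronasal masks and claustrophobia with total face masks. The second mask of a pair could then start on an already irritated site. At stake are the comfort ranking of the masks and any comparison of the two types.

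**Working it through.** The plan gives no alpha, power, effect size or SD for its 20 volunteers, so there is no sample-size figure to reproduce. The checks below read the draw as 50:50 at each step and repeated independently per volunteer. Both are assumptions.

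**1. Orders allowed.** Which type goes first (2) × order within A (2) × order within B (2) = 8. All orders of four masks: 4! = 24.

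**2. Expected position.** Each mask is in each of the four positions in 2 of the 8 orders, so the expected count is 20 × 2/8 = 5 in every mask-by-period cell. There is no systematic period bias.

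**3. Chance imbalance.** The number of volunteers starting with type A is Binomial(20, 0.5).
- P(10:10) = C(20,10)/2^20 = 184,756/1,048,576 = 0.176
- P(13:7 or worse, either direction) = 0.263
- P(14:6 or worse, either direction) = 0.115

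Eight orders cannot be used equally often by 20 volunteers (20/8 = 2.5). In 200,000 simulated draws of 20, every mask fell exactly five times in every period in about 0.06% of draws, and some mask-by-period cell held two or fewer in about 54%.

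**4. Effect on the type contrast.** With linear drift d per mask period, the first pair has mean position 1.5 and the second pair 3.5, so each volunteer's type difference shifts by 2d, with a sign set by which type came first. At 13:7 the net shift is 2d × (13 − 7)/20 = 0.6d. The documents give no d. For EtCO₂, an assumed range of 0.5 to 1 mmHg gives 0.3 to 0.6 mmHg.

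**5. Preceding mask.** Over the 8 orders, each mask follows its partner 4 times, follows each other-type mask once, and comes first twice. Over 20 volunteers this gives 40 same-type transitions out of 60, against 20 of 60 in a Williams square.

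**6. Carry-over illustration (assumed 20% of the previous mask's effect).**
- One mask differs by 3 from three equal masks, two-step draw: against its partner 3 − 0.2 × (4/8) × 3 = 2.70; against an other-type mask 3 − 0.2 × (1/8) × 3 = 2.93. Square: 3 − 0.2 × (1/4) × 3 = 2.85 for both.
- Both masks of one type lie 3 above both of the other, two-step draw: (3 + 0.2 × (4/8) × 3) − 0.2 × (2/8) × 3 = 3.30 − 0.15 = 3.15. Square: (3 + 0.2 × (1/4) × 3) − 0.2 × (2/4) × 3 = 3.15 − 0.30 = 2.85.

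**7. Precision.** Least-squares variances in units of the residual variance, 20 volunteers; the two-step figures are means over 400 simulated draws.

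| Model | Contrast | Two-step | Square | Ratio |
|---|---|---|---|---|
| Subject + period + mask | Type | 0.0534 | 0.0500 | 1.07 |
| Subject + period + mask | A1 vs A2 | 0.1064 | 0.1000 | 1.06 |
| Subject + period + mask | A1 vs B1 | 0.1063 | 0.1000 | 1.06 |
| As above + carry-over | Type | 0.0662 | 0.0550 | 1.20 |
| As above + carry-over | A1 vs A2 | 0.1850 | 0.1100 | 1.68 |
| As above + carry-over | A1 vs B1 | 0.1588 | 0.1100 | 1.44 |

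**The case against.** The case for leaving the draw alone is substantial. Which type goes first is randomised, so drift cancels in expectation, and what remains is the chance imbalance of any unrestricted randomisation. Most of the protection comes from a period term: once subject and period are fitted, the two-step draw costs only 6-7% in variance, about 3% in standard error. The documents give no drift or carry-over size, and there is a 5-minute washout. The EtCO₂ test is by EPAP level, which is set within each mask, so mask order is not tied to it. No test of EtCO₂ by mask is written. All of this stands, and it limits the point to an improvement in design.

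Three stronger readings are tempting, and the documents support none of them.
- A reader might infer that mask type is confounded with session half across the trial. That holds within a volunteer only. It would hold for the trial only if one draw served everyone, which the text neither says nor rules out.
- A reader might infer that carry-over falls more heavily on some masks. All four masks share the same pattern; what is uneven is which mask comes before.
- A reader might infer that the square reduces carry-over bias in the oronasal versus full-face contrast. In the illustration, 3.15 and 2.85 are equally far from 3, in opposite directions.

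What the objection does not answer is that the planned tests contain no period term, so as written nothing corrects an uneven split.

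**Conclusion.** The point holds as a cheap, worthwhile improvement; it does not demonstrate bias. Given a fair draw per volunteer, period balance is left to chance, with a 26% probability of a 13:7 or worse split in which type goes first. At 13:7, 0.6d of any linear drift remains in the unadjusted type contrast. If one draw served all volunteers, type and session half would be fully confounded, so the text should exclude that reading.

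The uneven mix of preceding masks is secondary. It matters only if an effect outlasts the washout, and it would then distort within-type and between-type comparisons by different amounts. The consequences reach the comfort test by mask and the stated comparison of types, not the EtCO₂ test by EPAP level. The sizes of d and of carry-over are assumptions, and the variance ratios assume a linear model with independent errors.

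**What to change.** State in Section 3 that order is allocated to each volunteer from a random list prepared in advance, using a four-sequence Williams square with five volunteers per sequence (4 × 5 = 20):

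- A1-A2-B2-B1
- A2-B1-A1-B2
- B1-B2-A2-A1
- B2-A1-B1-A2

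Each mask is then in each position five times, and each of the 12 ordered mask pairs occurs five times, provided all 20 complete. In Section 12, replace Kruskal-Wallis and Mann-Whitney for the mask comparison with a within-subject analysis that includes mask period.

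The cost is one rewritten Methods paragraph, a 20-line list and new text for the mask comparison in Section 12. No extra volunteers, visits or session time are needed. The gain is exact period balance. Relative to the square, the two-step draw has about 6-7% more variance with subject and period terms only. If a carry-over term is also fitted, the excess is roughly 20% for the type contrast and 40-70% for mask pairs.
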